5.0 Assessing major childhood disability in large perinatal RCTs by parent report

Although evaluation by trained assessors with tools like the Bayley Scales is a de facto 'gold-standard' for assessing disability, the predictive value and equivalence of BSID II and Bayley-III are the subject of ongoing research. We and others have defined cut-offs for major disability on BSID II and Bayley-III suitable for RCTs in cohorts that include Australian children.^{11,16,44,45}

However, assessor-administered scales have become prohibitively expensive in investigator-initiated, public-good perinatal trials that are large enough to change practice.^{11,46} Reliable, cost-effective measures of disability are essential to contain costs and maintain scientific validity in perinatal RCTs.^{44,45,47} Also, parent-administered scales may more accurately reflect infant behaviours, because they reflect observations over longer periods, and in more natural settings, than one-off evaluations by trained assessors in unfamiliar environments.

"Parent-completed assessments of children's abilities represent a more practical and cost-effective method for collecting longer-term outcome data in neonatal clinical trials ... than formal neurodevelopmental appraisals performed by trained assessors." ⁴⁴

We have therefore tested several measures of major disability using parent report. 11,13,14,44,45,48-50

5.1 Parent report in 3,493 children in the International Neonatal Immunotherapy Study (INIS)

In the INIS RCT, published in *New England Journal of Medicine*, ¹¹ we assessed cognitive delay at 2 years with the Parent Report of Children's Abilities–Revised (PARCA-R).^{48,49} Its parent report composite score (PRC) can range from 0-158, higher scores indicating higher function.⁴⁵ Before unblinded analysis, we derived a cut-off value for severe disability on the PARCA-R PRC score by calibrating it against the BSID II Mental Development Index (MDI) performed by trained assessors in a sub-cohort of Australian and New Zealand children, representing 17% of all survivors.^{11,45} The parent assessment successfully identified major cognitive delay. The area under the ROC curve (AUC) was >0.90 (a value of 1 indicating perfect prediction). A cut-point corresponding to a BSID II MDI score less than 3 SD below the norm for this sub-cohort was used to identify severe disability in the whole trial. Using a PARCA-R PRC cut-off of <2 SD below the sub-cohort norm to define major (i.e. moderate to severe) disability did not alter the conclusions. (Table S2, Supplementary Appendix, NEJM.org).¹¹ Importantly, different cut-offs do not affect the internal validity of comparisons in RCTs.

Page 59 of 81

5.2 Detecting major disability by parent report using the Ages and Stages Questionnaire ⁵⁰⁻⁵²

The Ages and Stages Questionnaire (ASQ)⁵³ is a widely validated tool completed by parents to assess development from one month to 5.5 years.^{13,14,52,53} Previous versions have been validated against BSID I and II to detect severe developmental delay in Australian children.^{54,55} We validated ASQ against concurrent evaluations for disability by trained assessors in about 1,000 children followed in the Magpie Trial of magnesium sulphate in pre-eclampsia.^{13,14,50,52} The correlation of ASQ and Bayley-III is higher after 18 months,⁵⁶ supporting our plan to assess children later.

We selected ASQ to assess disability in APTS because ASQ can be completed between 2-4 years (and between 2 and 5.5 years if necessary), unlike the PARCA-R,¹¹ which should be completed close to a child's 2nd birthday. It might be argued that using a parent report to detect disability could introduce bias, because parents know which intervention their child received and may have a strong preference. This is unlikely, however, because only parents with no strong preference for either study arm consent to join APTS. Also, using ASQ in a RCT like APTS (where within-centre randomisation tends to balance confounding variables evenly between study arms) is considerably less open to confounding than in non-randomised comparisons across centres or cohorts.

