1 SYNOPSIS

1.1 Primary clinical hypothesis:

An autologous transfusion of placental blood at birth will improve health outcomes in preterm babies born less than 30 weeks.

1.2 Study design:

This is a multicentre 2-arm parallel open label randomised controlled trial

1.3 Study interventions:

The two arms of the trial comprise:

- early cord clamping (which is the control arm) is clamping the cord within 10 secs of birth
- delayed cord clamping (for 60 seconds or more with the baby held below or at the level of the placenta)

1.4 Outcomes for the follow-up study:

Primary outcome Death and/or major disability at 24 months

Secondary outcomes Incidence of the following outcomes at 24 months:

- 1. Death
- 2. Major disability
- 3. Components of major disability
- 4. ASQ domain scores

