2.5 Outcome definitions

The primary outcome is death and/or major disability at 24 months corrected age. Assessments of major disability must be performed between 18 months to 27 months. Any data outside of this window will require a central review.

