Major problems with language or speech	Tier 1: SHSQ completed between 22-27 months (inclusive)	Unable to speak 10 words	Able to speak >10 words
	Tier 2: ASQ-3 completed after 18 months	Communication score indicative of delay (based on published ASQ cut-off)	Communication score not indicative of delay (based on published ASQ cut-off)
	Tier 3: Central review		
Cognitive delay	Tier 1: ASQ-3 completed after 18 months	Problem solving score indicative of delay (based on published ASQ cut-off)	Problem solving score not indicative of delay (based on published ASQ cut-off)
	Tier 2: Central review		

⁺ the windows given above for the determination of disability using the various sources were determined by clinicians involved in the APTS Follow-up study. All ages are corrected ages.

If the baby is alive and does not have one of the above major disabilities, and has been assessed for all of the above components, then they will be classified as alive and disability free. If the infant was alive and has no disability for CP, severe visual loss, deafness and major problems with language or speech, but missing information for cognitive delay, then the infant will be assumed to be alive and disability free at 2 years. Otherwise the infant will be considered as missing for the primary analysis.

Page 8 of 17

Page 72 of 81

APTS FU Statistical Analysis Plan v2.2

Table 6: Summary of completeness of the primary outcome and its components

Endpoint	Complete data	Missing data
Death or disability at 24 months		
Death status		
Cerebral palsy ⁺		
Severe visual loss+		
Deafness [†]		
Major problems with language or speech ⁺		
Cognitive delay ⁺		
hese analyses are restricted to those that were as	ssessed for these outcon	nes

Additionally, the baseline characteristics will be compared between those that have outcome data at 24 months versus those that have missing data at 24 months.

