2.8 Bayley-III and ASQ-3 calibration sub-study

The aim in this sub-study is to validate the cut-offs provided by ASQ-3 developers in the APTS population. The APTS follow-up study was able to obtain funding for a sample of children to be assessed using the Bayley-III. In this sample of children, the Ages and Stages Questionnaire (ASQ-3) published cut-offs will be calibrated against the Bayley-III definitions of developmental delay.

A stratified sampling approach was taken in order to obtain a high risk sample of developmentally delay in order to calibrate these two instruments. Additionally, some sites routinely perform Bayley-III, and therefore we were also able to obtain an opportunistic sample of babies with a Bayley-III and matching ASQ.

Table 11 below maps the ASQ domains to the Bayley-III scores. Scatterplots, spearman correlations and ROC analyses may be used to compare these scores.

Table 12: Mapping of ASQ-3 domains to Bayley-III scores.

ASQ-3 domains	Bayley-III scores
Problem solving	Cognitive
Communication	Communication
Gross motor	Motor scale – gross motor
Fine motor	Motor scale – fine motor
Personal-social	Social emotional

August 2020

Page 14 of 17

Page 78 of 81

APTS FU Statistical Analysis Plan v2.2

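### SAP v2.2 lets an unblinded parent report decide part of the primary outcome and plans no analysis showing whether a result depends on it

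*Supplement*

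**What the plan says.** SAP v2.2, section 1.2, describes the design: "This is a multicentre 2-arm parallel open label randomised controlled trial". Section 2.5 sets the endpoint: "The primary outcome is death and/or major disability at 24 months corrected age". Under section 2.5.2 one positive component makes a surviving child an event.

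Table 5 of the SAP assigns a source to each component:

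- **Cognitive delay:** "Tier 1: ASQ-3 completed after 18 months", with disability present when the entry reads "Problem solving score indicative of delay (based on published ASQ cut-off"). The only other tier is central review.
- **Cerebral palsy and language:** the SHSQ is Tier 1. The ASQ-3 is Tier 2 (a gross motor score of 0, or a communication score below the published cut-off).
- **Severe visual loss and deafness:** the SHSQ, then central review. There is no ASQ-3 tier.

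Protocol v4.0, section 3.4.4, says that parents complete the ASQ and a qualified health professional completes the SHSQ.

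The follow-up proposal (section 5.2) raises the objection itself, namely that "parents know which intervention their child received and may have a strong preference". It answers: "This is unlikely, however, because only parents with no strong preference for either study arm consent to join APTS". It adds that using the ASQ in a randomised trial "is considerably less open to confounding than in non-randomised comparisons across centres or cohorts".

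The SAP's one comparison of ASQ-3 with Bayley-III is in section 2.8: "Scatterplots, spearman correlations and ROC analyses may be used to compare these scores". Treatment arm is not mentioned there.

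**The concern.** Neither of the proposal's reasons addresses differential reporting. Having no strong preference describes parents before randomisation. It does not constrain how a parent who knows what was done at birth rates the child some two years later. Balanced confounders are a benefit of randomisation, but a difference between arms in how an outcome is reported arises afterwards and is a measurement problem.

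SAP v2.2 does not repeat that reasoning, but it keeps the ASQ-3 in the primary outcome. Sections 2.6.2 to 2.6.6 cover covariate adjustment, adherence, missing data, survival and causes of death; section 2.7 covers subgroups. None repeats the primary outcome without ASQ-3-decided items or compares ASQ-3 with Bayley-III by arm. If the composite differs mainly through cognitive delay, the planned output cannot say whether the children developed differently or were reported differently.

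**Working it through.** **1. The plan's own figures.** The proposal states 80% power for 1,320 infants, 30% against 21.5%, with 20% non-adherence. Diluting the difference gives 8.5 × 0.8 = 6.8 points. With 660 per arm, 30% against 23.2%, two-sided 0.05, power is 79.9%. The six scenarios in SAP Table 1, diluted by 0.7, give 78.6% to 79.3%. Both sets reproduce.

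**2. What a reporting shift would do if there were no true effect.** The documents give no rate of ASQ-3 delay, no size of shift and no overlap between components. Assumed:

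- a share p = 15% of survivors below the cut-off
- 90% survival
- 60% to 100% of those children with no other component
- 700 per arm
- a 35% composite rate (the 35% is one of the SAP Table 1 scenarios)
- normally distributed scores, with one arm's reports shifted by s SD.

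Spurious difference = [p − Φ(Φ⁻¹(p) − s)] × 0.9 × share with no other component.

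SE = √(2 × 0.35 × 0.65 / 700) = 0.0255. With b = difference / SE, type I error = P(Z > 1.96 − b) + P(Z < −1.96 − b).

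| Shift s | Rate below cut-off | Spurious difference (60% to 100%) | Type I error |
|---|---|---|---|
| 0.1 SD | 15% to 12.8% | 1.2 to 2.0 points | 7.5% to 12% |
| 0.2 SD | 15% to 10.8% | 2.3 to 3.8 points | 14% to 31.5% |

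Varying p from 10% to 20% at s = 0.2 widens the type I range to 10% to 44%. At the proposal's design (660 per arm, 30%), a purely reporting-based difference of 2, 3 or 4 points gives a significant result 13%, 23% or 37% of the time.

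**3. What the Bayley-III sample could show.** The proposal plans about 180 assessments. SAP 2.8 adds an opportunistic sample of unstated size. For the arm coefficient of ASQ-3 given Bayley-III, with correlation r (assumed 0.5 to 0.7) and n pairs split evenly:

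95% CI half-width = 1.96 × √(1 − r²) × 2 / √n, in SD units.

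- n = 180: r = 0.5 gives 1.96 × 0.866 × 2 / 13.42 = 0.25; r = 0.7 gives 1.96 × 0.714 × 2 / 13.42 = 0.21.
- n = 400 (illustrative): 0.17 to 0.14.

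At n = 180 the shift detectable with 80% power is 0.30 to 0.36 SD, and power for a 0.2 SD shift is 34% to 47%. The sample can exclude large shifts, but not shifts of the size used in step 2.

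**The case against.** The quoted reasoning comes from the 2014 funding proposal, where the ASQ came first for all major disability and the SHSQ was used only if the ASQ was unavailable. SAP v2.2 reversed that order for cerebral palsy, vision, hearing and language. Death cannot be misreported in this way. The cerebral palsy fallback needs a gross motor score of 0, a floor that a modest shift is unlikely to cross. Central review is blinded. Table 7 gives every component by arm, so a reader can see whether an effect sits only in cognitive delay. The type I figures need a shift in one direction, for which there is no evidence.

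All of this stands and narrows the exposure. It does not close it: blinded review does not blind the parent who filled in the form, and a Table 7 difference confined to cognitive delay fits a true effect and a reporting effect equally well.

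The remedies also have limits. Bayley-III is measured with error, so part of a real effect can stay in the arm coefficient. The documents do not say that Bayley-III assessors were blind to arm. Dropping ASQ-3 items drops cognitive delay. The account of the follow-up study's outcome in the summary of changes also allows cerebral palsy, visual loss and deafness to come from parent report, so the source behind each SHSQ entry needs checking.

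**Conclusion.** The gap is real and inexpensive to close. SAP v2.2 relies on an unblinded parent report for one component outright and for two as a fallback, and it has no analysis showing whether a primary-outcome difference depends on those items.

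A reader might infer more, and the documents do not support three such readings. First, they do not show that reporting bias occurred or in which direction; 7.5% to 31.5% illustrates what follows from assumed shifts of 0.1 to 0.2 SD. Second, the Bayley-III sample could not settle the question: at about 180 pairs its half-width of 0.21 to 0.25 SD exceeds those shifts. Third, most of the composite does not rest on parent report by design, since death and four SHSQ-first components have other primary sources. The design is not invalid; what is missing is a robustness analysis that would change how far a positive result can be taken.

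**What to change.** 1. **SAP 2.6, main change.** Pre-specify one sensitivity analysis of the primary outcome with the same GEE model. Count death, or cerebral palsy, severe visual loss, deafness or language disability established from the health-professional SHSQ only, with nothing decided by the ASQ-3. State in advance that it omits cognitive delay and has fewer events, and that a smaller effect could mean either bias removed or a true cognitive effect lost.
2. **SAP 2.8, supportive.** After the blinded cut-off work is final and the database is released, take all paired ASQ-3 and Bayley-III assessments whose assessors are confirmed blind to arm. For each mapped domain, regress ASQ-3 on Bayley-III, arm and gestation stratum, and report the arm coefficient with its 95% CI. Say that a null result excludes only large shifts, and that Bayley-III measurement error prevents reading a non-zero coefficient as pure reporting bias.

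Cost: SAP wording, two secondary analyses on data already collected, and a check on assessor blinding. The blinded calibration in protocol section 3.4.4 is preserved, because arm enters only after release. The primary analysis is unchanged; the sensitivity composite will have a wider interval.

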6.0 International collaboration: the UK CORD Trial and a planned prospective meta-analysis

[name], who is a CI both on APTS Grant ID 571309 and on the current application, is also the principal investigator of the UK CORD Trial Collaboration. This is funded by the UK National Institutes of Health Research to undertake (i) a parallel multicentre trial of deferred cord clamping in very preterm infants in the UK⁵⁷ and (ii) a collaborative, individual patient meta-analysis ⁵⁸⁻⁶⁰ of the UK CORD Trial, APTS and similar trials of enhanced placental transfusion. The Trial Management Committees of APTS, CORD and other trials will share their data after publication. These trials will produce a meta-analysis of a few thousand infants, similar to our NeOProM Collaboration, ⁵⁹ substantially enhancing the precision of future comparisons of childhood outcome and in-hospital mortality.

RESEARCH PLAN – METHODS AND TECHNIQUES TO BE USED

AIM: To determine whether, compared with deferred cord clamping (DCC), early clamping improves survival without major disability in children who were born < 30 weeks gestation.

Primary outcome: *(for which new funds are now sought, as stated in the initial proposal)* Survival without major disability at 2-3 years

Major disability is defined by a positive result on;

- (iii) parent report on the Ages and Stages Questionnaire (ASQ),* ^{13,14} or, if ASQ is unavailable,
- (iv) a modified Short Health Status Questionnaire completed by a medically qualified practitioner ^{11,15} documenting either:-
 - (e) major developmental delay, including language or speech problems, or
 - (f) cerebral palsy with inability to walk unassisted at or after 2 yrs corrected age, or
 - (g) severe visual loss (cannot fixate/ legally blind, or corrected acuity <6/60 in both eyes), or
 - (h) deafness, requiring a hearing aid or cochlear implants.

* using a cut-off score on ASQ equivalent to 2 SDs below the trial norm for cognitive scores on the Bayley-III Scales of Infant and Toddler Development (Bayley-III),¹⁶ derived from Bayley-III results within the study, performed by trained assessors in a random sub-cohort of 15% of surviving children stratified with equal numbers <27 or \geq 27 weeks gestation.

II: Secondary outcomes (for which new funds are now sought, as stated in the initial proposal)

- (1) Death at any time up to 3 years.
- (2) Components of major disability at 3 years.
- (3) ASQ overall and domain scores

III: Tertiary outcomes (already funded in Grant ID 571309: no new funding requested)

Page 60 of 81

Short term outcomes including in-hospital mortality and morbidity at 36 weeks corrected gestation. **Eligibility:**

The sole eligibility criterion is enrolment in the APTS trial, which included parental consent for childhood follow up to 3 years. (Specific eligibility criteria for recruitment to APTS were: mothers imminently delivering babies of 29⁶ weeks gestation or less; informed consent received from a parent; no indication or contraindication to placental transfusion, in view of parent or doctor).

Intervention:

- (a) immediate cord clamping (< 10 seconds after birth)
- (b) deferred cord clamping (≥ 60 seconds after birth)

Sample size and power:

1,320 infants gives 80% power to show a decrease of 8.5% in the primary outcome, from 30% to 21.5%, with two tailed significance of p <0.05, based on a non-adherence rate of 20% (5% in the early clamping group and 15% in the deferred cord clamping group).

Predefined subgroups:

Gender: male or female

Gestational age: infants of 26 6 weeks gestation or less or 27 0 weeks gestation or more

Statistical analysis:

[name], NHMRC Clinical Trials Centre, is statistical lead. Using similar methodology as in our *New England Journal of Medicine* study,¹¹ before unblinding, ASQ scores will be calibrated against Bayley-III cognitive scores obtained concurrently by trained assessors in a random sample (stratified by gestation at birth) of 15% of survivors aged 2 to 3 years (n = ~180). Assuming a 20% event rate and a true area under the ROC curve (AUC) of 0.89 (similar to the result of our previous analysis with the PARCA-R,^{11,45}) a sample of N=180 would yield an estimate of AUC with a 95% confidence interval ranging from 0.83 to 0.93. A cut-off score on ASQ corresponding to 2SD below the Bayley-III norm for the sample (i.e. moderate to severe delay) will be applied to the whole trial.

Comparisons between treatment arms on pre-specified endpoints will be undertaken at the two-sided 5% level of significance according to the intention-to-treat analysis principle. Binary endpoints will be analysed by two-sided chi-squared tests. Continuous variables (e.g. ASQ score) will be compared by t-tests or non-parametric equivalent as necessary. Treatment effects adjusted for baseline characteristics will be estimated in a series of sensitivity analyses using a general linear modelling approach. These methods will also be used to identify clinically important prognostic factors and heterogeneity in subgroup analyses. No adjustments will be made for multiple comparisons, but secondary analyses will be interpreted in proper context.

Independent Data and Safety Monitoring Committee:

An Independent Data and Safety Monitoring Committee (IDSMC) is monitoring the progress of all aspects of APTS recruitment and subsequent childhood follow up to ensure that they meet the highest standards of ethics and patient safety. It is also reviewing interim data and other emerging evidence, including relevant RCTs and overviews of RCTs. During the recruitment phase, the IDSMC will advise the TMC if in their view there is proof beyond reasonable doubt of net clinical benefit or harm for all infants, or for a subset of infants, that might be expected to influence the management of many clinicians. Data on study outcomes are being monitored annually, or more often if requested by the IDSMC, to ensure safety and that event rates meet protocol projections.

Feasibility, teamwork and collaboration:

We anticipate no problem in recruiting and following up the planned subjects. Ethics approval and parental consent have been obtained. The CIs and AIs have a strong record of teamwork and collaboration in trials, cohort and follow up studies in Australia, New Zealand and overseas, funded

Page 61 of 81

by NHMRC, NZ HRC, UK MRC, UK DFID, WHO and others, with publications in *New England Journal of Medicine, Lancet*^{4,11,12, 17-20,50,61,62} and other peer-reviewed journals.^{3,6,13,14,23,44,45,48,49,63}

Expected results:

Our hypothesis is that DCC will improve the primary outcome of death or major disability on follow up, with no increase in major disability or in any of its components, including cerebral palsy. DCC will improve the secondary outcomes of (i) mortality and (ii) disability and (iii) ASQ score.

Limitations:

Although we have already validated the PARCA-R parent report against BSID II ^{11,45} and Bayley-III⁴⁴ in high risk newborn Australian and New Zealand infants across a wide range of gestational ages in our *NEJM* report,¹¹ the PARCA-R must be completed close to the child's second birthday, corrected for gestation, and some children will have passed this age during follow up in this project.

However, we have also validated the Ages and Stages Questionnaire (ASQ) against specialist evaluations by trained assessors in a large cohort of survivors in the Magpie Trial. ^{13,14,50,52} The ASQ can be used between one month and 5.5 years, and is thus appropriate for calibration against Bayley-III in this study, using similar methods, ¹¹ (see section 5.2 and Statistical Analysis, p 8).

MILESTONES & PLANNING

A four year time span is needed to achieve the aims of the project.

	2015	2016	2017	2018
Finalise Manual of Operations and study materials	Х			
Recruit coordinating centre staff	Х			
Appoint local follow up staff, begin follow up	XXXX	XXXX	XXXX	XX
Expected numbers of infants followed up each year	156	214	390	440
Analysis, writing up and publication				XX

OUTCOMES, INNOVATION & SIGNIFICANCE

- In acknowledgement of the scientific importance of the NHMRC APTS project and its significance for global practice, CIA has been commissioned by the Editor of the American Journal of Obstetrics and Gynecology, a global opinion-leading journal with a circulation of 45,000, to submit an open access Clinical Opinion and commentary, co authored with other CIs, AIs and collaborators, describing the background and rationale of the NHMRC APTS project, entitled "Timing of clamping of the umbilical cord in very preterm infants."
- The NHMRC APTS project will provide insight into the development of reliable, cost-effective methods of follow up in perinatal trials, by calibrating the Ages and Stages Questionnaire, based on parent report, against the Bayley-III Scales of Infant Development, performed by trained assessors, in a sub-cohort of the trial population, as we did with the PARCA-R parent report in the *New England Journal of Medicine*.¹¹ As event rates fall and trial sample sizes rise, this will be increasingly important in ensuring scientifically valid and financially and logistically viable methods of childhood follow up in large populations in investigator-initiated, public-good trials.
